### **11.2 Methods for Evaluation of Measurable Disease:**

All baseline evaluations should be performed as closely as possible to the beginning of treatment.

The same method of assessment and the same technique should be used to characterize each identified and reported lesion at baseline and during follow-up. Imaging-based evaluation is preferred to evaluation by clinical examination when both methods have been used to assess the anti-tumor effect of a treatment.

Clinical lesions: Clinical lesions will only be considered measurable when they are superficial (e.g., skin nodules and palpable lymph nodes). For the case of skin lesions, documentation by color photography, including a ruler to estimate the size of the lesion, is recommended.

Conventional CT: These techniques should be performed with cuts of 10 mm or less in slice thickness contiguously. Spiral CT should be performed using a 5 mm contiguous reconstruction algorithm. Although CT scan is the preferred imaging modality for this study, MRI or PET/CT will also be considered acceptable. Images of the Chest, Neck, Abdomen and Pelvis are required at each timepoint listed in the study calendar.

PET/CT: For patients with Richter's Syndrome, PET/CT evaluation is preferred over contrast CT, though the latter can be used if necessary.

CONFIDENTIAL

This document is confidential. Do not disclose or use except as authorized.

### **11.3 Response Criteria**

Response and progression will be evaluated in this study using the 2008 IW-CLL criteria for CLL (Hallek et al., 2008) or for RS by Lugano criteria (Cheson et al., 2014).

If a bone marrow biopsy was done to confirm a response, sites may use the blood MRD results within 2 months of the biopsy to confirm that MRD status.

#### **11.3.1 2008 IW-CLL Criteria ( CLL/SLL patients only)**

##### **11.3.1.1 Complete Remission (CR):**

- Evaluation of Non-Target Lesions CR requires all of the following criteria: Peripheral blood lymphocytes (evaluated by blood and differential count) below  $4 \times 10^9/L$  ( $4,000/\mu L$ ). The presence of minimal residual disease (MRD) after therapy should be assessed. The sensitivity of the method used to evaluate for MRD should be reported.
- Absence of significant lymphadenopathy (eg, lymph nodes  $>1.5$  cm in diameter) by physical examination. A CT scan of the abdomen, pelvis, and thorax is desirable if previously abnormal. Lymph nodes should not be larger than 1.5 cm in diameter.
- No hepatomegaly or splenomegaly by physical examination. A CT scan of the abdomen should be performed at response assessment if found to be abnormal before therapy or if physical examination is inconclusive at the time of evaluation.
- Absence of constitutional symptoms.
- Blood counts above the following values: Neutrophils more than  $1.5 \times 10^9/L$  ( $1,500/\mu L$ ) without need for exogenous growth factors, Platelets more than  $100 \times 10^9/L$  ( $100,000/\mu L$ ) without need for exogenous growth factors, Hemoglobin more than 110 g/L (11.0 g/dL) without red blood cell transfusion or need for exogenous erythropoietin.
- Bone marrow sample must be at least normocellular for age, with less than 30% of nucleated cells being lymphocytes. Lymphoid nodules should be absent.

##### **11.3.1.2 Complete Response with incomplete marrow recovery (CRi):**

- Complete response as defined above, but without normal blood counts.

##### **11.3.1.3 Minimal Residual Disease:**

CONFIDENTIAL

This document is confidential. Do not disclose or use except as authorized.

- Patients with CR or CRi or patients with PR with resolution of lymphocytosis will be assessed for minimal residual disease (MRD) at every three months. Such patients who have fewer than 0.01% ( $10^{-4}$ ) CLL cell percentage of leukocytes in the bone marrow, as assessed by four-color flow cytometry, will be considered to be MRD negative.

#### 11.3.1.4 **Partial Response (PR):**

- A decrease in the number of blood lymphocytes by 50% or more from the value before therapy.
- Reduction in lymphadenopathy as defined by the following:
  - A decrease in lymph node size by 50% or more either in the sum products of up to 6 lymph nodes, or in the largest diameter of the enlarged lymph node(s) detected prior to therapy.
  - No increase in any lymph node, and no new enlarged lymph node. In small lymph nodes (< 2 cm), an increase of less than 25% is not considered to be significant.
- A reduction in the noted pretreatment enlargement of the spleen or liver by 50% or more
- The blood count should show one of the following results: Neutrophils more than  $1.5 \times 10^9/L$  (1,500/ $\mu$ L) without need for exogenous growth factors, Platelet counts greater than  $100 \times 10^9/L$  (100,000/ $\mu$ L) or 50% improvement over baseline without need for exogenous growth factors, Hemoglobin greater than 110 g/L (11.0 g/dL) or 50% improvement over baseline without requiring red blood cell transfusions or exogenous erythropoietin.

#### 11.3.1.5 **Nodular Partial Response (nPR):**

- All criteria for CR are met, but lymphoid nodules can be found in the bone marrow biopsy. Note, if flow cytometry and immunohistochemistry are negative for a clonal B-cell population then these patients can be considered as CR or CRi.

#### 11.3.1.6 **Partial Response with Lymphocytosis (PR-L):**

- Evidence of a radiographic PR but persistent lymphocytosis with >5,000 B-lymphocytes per  $\mu$ L where the absolute lymphocyte count has not decreased by 50% or more compared to baseline are considered to have a PR with lymphocytosis.

#### 11.3.1.7 **Progressive Disease:**

- Progressive disease during or after therapy is characterized by at least one of the following:
  - Lymphadenopathy: Progression of lymphadenopathy is often discovered by physical examination and should be recorded. For CT scans used to

CONFIDENTIAL

This document is confidential. Do not disclose or use except as authorized.

confirm progression or relapse of lymphadenopathy, progression is defined as:

- An increase by 50% or more in greatest determined diameter of any previous site.
- An increase in the previously noted enlargement of the liver or spleen by 50% or more or the de novo appearance of hepatomegaly or splenomegaly.
- An increase in the number of blood lymphocytes by 50% or more with at least 5,000 B lymphocytes per microliter (Note: because of the well-described lymphocyte redistribution phenomenon, any increase in lymphocyte count during duvelisib monotherapy or any increase during combination therapy in the setting of improvement of lymph nodes or cytopenias will not be considered disease progression)
- Transformation to a more aggressive histology (i.e., Richter syndrome). This diagnosis must be established by lymph node biopsy.
- Occurrence of cytopenias (neutropenia, anemia, or thrombocytopenia) due to CLL.
  - During therapy, cytopenias cannot be used to define disease progression.
  - After therapy, the progression of any cytopenia (unrelated to autoimmune cytopenia), as documented by a decrease of Hb levels by more than 20 g/L (2 g/dL) or to less than 100 g/L (10 g/dL), or by a decrease of platelet counts by more than 50% or to less than  $100 \times 10^9/L$  (100,000/ $\mu$ L), which occurs at least 3 months after treatment, defines disease progression, if marrow biopsy demonstrates an infiltrate of clonal CLL cells.

11.3.1.8 **Stable Disease:** Patients who have not achieved a CR or a PR, and who have not exhibited progressive disease, will be considered to have stable disease.

11.3.1.9 **Treatment Failure:** Responses that should be considered clinically beneficial include CR and PR; all others (eg, stable disease, nonresponse, progressive disease, or death from any cause) should be rated as a treatment failure.

11.3.1.10 **Relapse:** Relapse is defined as a patient who has previously achieved the above criteria of a CR or PR, but after a period of 6 or more months, demonstrates evidence of disease progression.

11.3.1.11 **Refractory Disease:** Refractory disease is defined as treatment failure or disease progression within 6 months to the last anti-leukemic therapy.

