New lesions	New FDG-avid foci consistent with lymphoma rather than another etiology (eg, infection, inflammation). If uncertain regarding etiology of new lesions, biopsy or interval scan may be considered	Regrowth of previously resolved lesions A new node > 1.5 cm in any axis A new extranodal site > 1.0 cm in any axis; if < 1.0 cm in any axis, its presence must be unequivocal and must be attributable to lymphoma Assessable disease of any size unequivocally attributable to lymphoma
Bone marrow	New or recurrent FDG-avid foci	New or recurrent involvement

- Abbreviations: 5PS, 5-point scale; CT, computed tomography; FDG, fluorodeoxyglucose; IHC, immunohistochemistry; LDi, longest transverse diameter of a lesion; MRI, magnetic resonance imaging; PET, positron emission tomography; PPD, cross product of the LDi and perpendicular diameter; SDi, shortest axis perpendicular to the LDi; SPD, sum of the product of the perpendicular diameters for multiple lesions.

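### The CLL/SLL progression list has no item for new enlarged lymph nodes, so read literally it can delay recorded nodal progression by at least one scan interval and bias PFS and duration of response upward

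*Combined protocol and SAP*

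**What the plan says.** Section 11.3 names the governing source: "Response and progression will be evaluated in this study using the 2008 IW-CLL criteria for CLL". Section 11.3.1 then writes out its own definitions for CLL/SLL.

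- **Progressive disease (11.3.1.7).** At least one listed item must be met. The nodal item opens with "Progression of lymphadenopathy is often discovered by physical examination and should be recorded", and then defines progression on CT as "An increase by 50% or more in greatest determined diameter of any previous site". The other items are growth of the liver or spleen "or the de novo appearance of hepatomegaly or splenomegaly", a rise in blood lymphocytes, transformation, and cytopenias.
- **Partial response (11.3.1.4).** It requires "No increase in any lymph node, and no new enlarged lymph node".
- **Complete remission (11.3.1.1).** "Lymph nodes should not be larger than 1.5 cm in diameter".
- **Stable disease (11.3.1.8).** This is the residual class: "Patients who have not achieved a CR or a PR, and who have not exhibited progressive disease, will be considered to have stable disease".

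For Richter's patients only, the Lugano table in 11.3.2 lists "A new node > 1.5 cm in any axis" under progressive disease. Section 11.3.4 has all scans read centrally, with the radiographic result sent to sites for data entry. Under 11.3.3 a PFS event is progression or death, and patients alive without progression are censored at the last disease evaluation. Section 13.3 ends duration of response (DOR) at progression and estimates PFS and DOR by Kaplan-Meier.

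**The concern.** A node that was not there before is not a previous site, so the CT rule does not reach it, and nothing else in the CLL/SLL list does. The gap is conspicuous because the same list counts newly appearing liver or spleen enlargement, and the PR definition treats a new enlarged node as disqualifying. A central reader who applies the written CT rule has no item under which to record the node as progression.

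At stake are the dates, and for some patients the occurrence, of progression events in PFS and DOR. Both are single-arm estimates with no control arm in which the same error would partly cancel.

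**Working it through.** The plan states no PFS target, power or sample size for PFS, so there is no figure of its own to reproduce. The check applies the written rules to one patient, then works out the delay.

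**Step 1: score one patient.** Take a CLL/SLL patient whose only change at a scan is a new enlarged node above 1.5 cm.

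- CR (11.3.1.1): ruled out by the 1.5 cm limit.
- PR (11.3.1.4): ruled out by the new-node condition.
- PD (11.3.1.7): no previous site has grown by 50%; liver, spleen, lymphocytes, histology and counts are unchanged. No item is met.

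| Patient | As written | With a new-node item |
|---|---|---|
| No prior CR or PR | Stable disease (11.3.1.8) | PD at this scan |
| Prior CR or PR | Not PD; 11.3.1.8 does not apply | PD at this scan |

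In both rows no PFS event is recorded at that scan as written. In the second row the response also continues for DOR.

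**Step 2: the delay.** At the next scan the node is a previous site and counts once it has grown by 50% or more. Scans fall at C4, C7 and C13, then about every 6 cycles or at the investigator's discretion (Synopsis; section 5; Table 9 notes). A cycle is 28 days, with cycle 1 up to 49 days (5.1.1).

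- C4 to C7: 3 × 28 = 84 days (84 / 30.4375 = 2.8 months).
- C7 to C13, and each later 6-cycle interval: 6 × 28 = 168 days (5.5 months).

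The length of cycle 1 shifts every scan but not these intervals. They are nominal: the calendar allows windows around each scan.

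**Step 3: what this could do to PFS (illustration on assumed values).** Let q be the share of PFS events that first show as a new node only, and S the true PFS curve. Assume that every event is dated at the first scan on or after it occurs, and that new-node-only events are dated exactly one scan later. With a 49-day cycle 1, scans fall on days 105, 189, 357, 525 and 693 (49 + 28 × 2, 5, 11, 17 and 23). The last scan before 12 months is day 357, and before 24 months day 693, so

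- overstatement at 12 months = q × [S(189) − S(357)];
- overstatement at 24 months = q × [S(525) − S(693)].

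Assume S(t) = 2^(−t/m), with median m of 13.3, 22 or 36 months and q from 10% to 30%. The first two medians are PFS figures that the Background reports for other treatments or populations; 36 and the range of q are pure assumptions.

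| m (months) | S(189) − S(357) | 12-month, q = 10% to 30% | S(525) − S(693) | 24-month, q = 10% to 30% |
|---|---|---|---|---|
| 13.3 | 0.181 | 1.8 to 5.4 points | 0.102 | 1.0 to 3.1 points |
| 22 | 0.131 | 1.3 to 3.9 points | 0.093 | 0.9 to 2.8 points |
| 36 | 0.089 | 0.9 to 2.7 points | 0.072 | 0.7 to 2.2 points |

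**Step 4: the primary endpoint.** A node above 1.5 cm already rules out CR, and CRi (11.3.1.2) carries the same nodal condition. The 12/35 two-stage rule in 13.2 therefore does not depend on the gap. ORR at that assessment is also unaffected, because PR excludes new enlarged nodes.

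**The case against.** The strongest reply is that the list is only a restatement. Section 11.3 names the 2008 IW-CLL criteria, and nothing says that 11.3.1.7 overrides them. The examination sentence is not limited to previous sites, and section 11.2 accepts palpable nodes as measurable. An investigator could therefore call a new palpable node progression. This stands in part: the bias arises only where readers follow the written list. But the protocol does not say which text governs, the examination sentence gives no threshold and does not mention new nodes, and 11.2 prefers imaging when both methods are used. What the cited publication says about new nodes cannot be checked from the documents and is not assumed here.

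A reader might infer several stronger points that the documents do not support.

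- **Every such patient is scored stable.** That fits only patients without a prior CR or PR.
- **A definite inflation of PFS.** One could take the 72% 12-month PFS in the Background and remove 10% to 20% of the hazard: h = −ln 0.72 = 0.3285, exp(−0.9h) = 0.744, exp(−0.8h) = 0.769. But the 72% comes from a venetoclax study in del(17p) CLL, the share is assumed, the hazard includes deaths, and the calculation deletes events that the written rule would often only delay.
- **The two cohorts become incomparable.** Section 11.3 deliberately assigns different criteria to the two diseases, and 13.3 plans no comparison of PFS between them. The Lugano entry shows only that the protocol states a new-node rule where it means to have one.

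**Conclusion.** The gap is real and can be verified from the text. Followed literally, 11.3.1.7 gives no progression at the scan that first shows a new enlarged node, and nodal progression is dated at the earliest one scheduled scan later: nominally 84 or 168 days. Another progression item or death can come first and shorten the delay. A node that does not grow by 50% lengthens it. Some events may be lost rather than delayed, since active follow-up off treatment ends when other CLL therapy starts (5.5).

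The direction is upward for PFS and, in responders, for DOR. The amount cannot be derived, because the documents give neither the share of progressions that first show as new nodes nor a PFS assumption for this regimen. The range of about 1 to 5 points at 12 months and 1 to 3 at 24 months is an illustration, not an estimate. Both endpoints are secondary and untested, and the primary CR analysis stands as it is. The correction is worth making because it is cheap and a stated rule otherwise gives the wrong event date.

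**What to change.** Add an item to 11.3.1.7 for the appearance of new enlarged lymph nodes, with a stated size threshold consistent with the 1.5 cm nodal limit already used in 11.3.1.1. The threshold must be written out, because 11.3.1.4 gives no size for a new node; its 2 cm wording concerns growth of small nodes. Then reconcile 11.3, 11.3.1.4 and 11.3.1.7, and say whether the written list or the cited IW-CLL criteria govern where they differ. The central readers should work from the same text.

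The cost is one list item and one sentence, plus a check of CLL/SLL scans already read for new nodes not recorded as progression. The downside is slightly less favourable PFS and DOR.

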### 11.3.2 2014 Lugano Criteria (Richter's Patients Only):

CONFIDENTIAL

This document is confidential. Do not disclose or use except as authorized.

Response and Site	PET-CT–Based Response	CT-Based Response
Complete	Complete metabolic response	Complete radiologic response (all of the following)
Lymph nodes and extralymphatic sites	Score 1, 2, or 3* with or without a residual mass on 5PS ‡	Target nodes/nodal masses must regress to ≤ 1.5 cm in LDi
	It is recognized that in Waldeyer's ring or extranodal sites with high physiologic uptake or with activation within spleen or marrow (eg, with chemotherapy or myeloid colony-stimulating factors), uptake may be greater than normal mediastinum and/or liver. In this circumstance, complete metabolic response may be inferred if uptake at sites of initial involvement is no greater than surrounding normal tissue even if the tissue has high physiologic uptake	No extralymphatic sites of disease
Nonmeasured lesion	Not applicable	Absent
Organ enlargement	Not applicable	Regress to normal
New lesions	None	None
Bone marrow	No evidence of FDG-avid disease in marrow	Normal by morphology; if indeterminate, IHC negative
Partial	Partial metabolic response	Partial remission (all of the following)
Lymph nodes and extra-lymphatic sites	Score 4 or 5 ‡ with reduced uptake compared with baseline and residual mass(es) of any size	≥ 50% decrease in SPD of up to 6 target measurable nodes and extranodal sites
	At interim, these findings suggest responding disease	When a lesion is too small to measure on CT, assign 5 mm × 5 mm as the default value
	At end of treatment, these findings indicate residual disease	When no longer visible, 0 × 0 mm
		For a node > 5 mm × 5 mm, but smaller than normal, use actual measurement for calculation
Nonmeasured lesions	Not applicable	Absent/normal, regressed, but no increase
Organ enlargement	Not applicable	Spleen must have regressed by > 50% in length beyond normal
New lesions	None	None

CONFIDENTIAL

This document is confidential. Do not disclose or use except as authorized.

Response and Site	PET-CT–Based Response	CT-Based Response
Bone marrow	Residual uptake higher than uptake in normal marrow but reduced compared with baseline (diffuse uptake compatible with reactive changes from chemotherapy allowed). If there are persistent focal changes in the marrow in the context of a nodal response, consideration should be given to further evaluation with MRI or biopsy or an interval scan	Not applicable
No response or stable disease	No metabolic response	Stable disease
Target nodes/nodal masses, extranodal lesions	Score 4 or 5 with no significant change in FDG uptake from baseline at interim or end of treatment	< 50% decrease from baseline in SPD of up to 6 dominant, measurable nodes and extranodal sites; no criteria for progressive disease are met
Nonmeasured lesions	Not applicable	No increase consistent with progression
Organ enlargement	Not applicable	No increase consistent with progression
New lesions	None	None
Bone marrow	No change from baseline	Not applicable
Progressive disease	Progressive metabolic disease	Progressive disease requires at least 1 of the following
Individual target nodes/nodal masses	Score 4 or 5 with an increase in intensity of uptake from baseline and/or	PPD progression:
Extranodal lesions	New FDG-avid foci consistent with lymphoma at interim or end-of-treatment assessment	An individual node/lesion must be abnormal with: LDi > 1.5 cm and Increase by $\geq$ 50% from PPD nadir and An increase in LDi or SDi from nadir 0.5 cm for lesions $\leq$ 2 cm 1.0 cm for lesions > 2 cm In the setting of splenomegaly, the splenic length must increase by > 50% of the extent of its prior increase beyond baseline (eg, a 15-cm spleen must increase to > 16 cm). If no prior splenomegaly, must increase by at least 2 cm from

CONFIDENTIAL

This document is confidential. Do not disclose or use except as authorized.

Response and Site	PET-CT–Based Response	CT-Based Response
		baseline New or recurrent splenomegaly
Nonmeasured lesions	None	New or clear progression of preexisting nonmeasured lesions
New lesions	New FDG-avid foci consistent with lymphoma rather than another etiology (eg, infection, inflammation). If uncertain regarding etiology of new lesions, biopsy or interval scan may be considered	Regrowth of previously resolved lesions A new node > 1.5 cm in any axis A new extranodal site > 1.0 cm in any axis; if < 1.0 cm in any axis, its presence must be unequivocal and must be attributable to lymphoma Assessable disease of any size unequivocally attributable to lymphoma
Bone marrow	New or recurrent FDG-avid foci	New or recurrent involvement

- Abbreviations: 5PS, 5-point scale; CT, computed tomography; FDG, fluorodeoxyglucose; IHC, immunohistochemistry; LDi, longest transverse diameter of a lesion; MRI, magnetic resonance imaging; PET, positron emission tomography; PPD, cross product of the LDi and perpendicular diameter; SDi, shortest axis perpendicular to the LDi; SPD, sum of the product of the perpendicular diameters for multiple lesions.
- ¶\* A score of 3 in many patients indicates a good prognosis with standard treatment, especially if at the time of an interim scan. However, in trials involving PET where de-escalation is investigated, it may be preferable to consider a score of 3 as inadequate response (to avoid undertreatment). Measured dominant lesions: Up to six of the largest dominant nodes, nodal masses, and extranodal lesions selected to be clearly measurable in two diameters. Nodes should preferably be from disparate regions of the body and should include, where applicable, mediastinal and retroperitoneal areas. Non-nodal lesions include those in solid organs (eg, liver, spleen, kidneys, lungs), GI involvement, cutaneous lesions, or those noted on palpation. Nonmeasured lesions: Any disease not selected as measured, dominant disease and truly assessable disease should be considered not measured. These sites include any nodes, nodal masses, and extranodal sites not selected as dominant or measurable or that do not meet the requirements for measurability but are still considered abnormal, as well as truly assessable disease, which is any site of suspected disease that would be difficult to follow quantitatively with measurement, including pleural effusions, ascites, bone lesions, leptomeningeal disease, abdominal masses, and other lesions that cannot be confirmed and followed by imaging. In Waldeyer's ring or in extranodal sites (eg, GI tract, liver, bone marrow), FDG uptake may be greater than in the mediastinum with complete metabolic response, but should be no higher than surrounding normal physiologic uptake (eg, with marrow activation as a result of chemotherapy or myeloid growth factors).
- ¶† PET 5PS: 1, no uptake above background; 2, uptake ≤ mediastinum; 3, uptake > mediastinum but ≤ liver; 4, uptake moderately > liver; 5, uptake markedly higher than liver and/or new lesions; X, new areas of uptake unlikely to be related to lymphoma.

CONFIDENTIAL

This document is confidential. Do not disclose or use except as authorized.

